#### Fasting conditions

- For Visits 3 (Day 1), 6 (Week 8), 7 (Week 12), 10 (Week 30), 12 (Week 43), and 14 (Week 56), participants need to come to the study center in a fasting condition after an overnight fast of no less than 8 hours which consists of no food or liquid intake, other than water. The participants should not take any antidiabetic medication before blood sampling.
- Fasting (before breakfast and before administration of antidiabetic medication) self-monitored plasma glucose (SMPG) must be performed per SoA ([Section 1.3](#)).

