**Table 3 - Rescue criteria**

Time in Study	Threshold
From randomization up through the scheduled Week 8 visit (Visit 6)	FPG >15.0 mmol/L (>270 mg/dL)
After the Week 8 visit (Visit 6) up through the scheduled Week 12 visit (Visit 7)	FPG >13.3 mmol/L (>240 mg/dL)
After the Week 12 visit (Visit 7) through the end of Week 30 visit (Visit 10)	FPG >11.1 mmol/L (>200 mg/dL) or HbA1c ≥8.5%
After the Week 30 visit (Visit 10) through the end of the treatment period (Week 56 [Visit 14])	FPG >10.1 mmol/L (>180 mg/dL) or HbA1c ≥8.0%

FPG: fasting plasma glucose, HbA1c: hemoglobin A1c

Routine fasting SMPG and central laboratory alerts on FPG (and HbA1c at Week 12 [Visit 7] onwards) will be set up to ensure that glycemic parameter results remain below the predefined thresholds.

- If a fasting SMPG value exceeds the specific glycemic limit on 1 day, the participant must check it again during the following 2 days. If all the SMPG values in 3 consecutive days exceed the specific limit, the participant should contact the Investigator and a central laboratory FPG measurement (and HbA1c from Week 12 [Visit 7] onwards) should be performed as soon as possible for confirmation.
- Upon receipt of a central laboratory alert for either FPG or HbA1c, a central laboratory re-test must be completed and confirmed as exceeding the threshold for rescue before rescue therapy is initiated. The re-test confirmation should be performed as soon as possible during an unscheduled visit.

In the event that a confirmatory FPG and/or HbA1c value exceeds the threshold, the Investigator should ensure that no reasonable explanation exists for insufficient glucose control and in particular that:

- The increased FPG has been tested at a fasting status (ie, no food or liquid intake [except water] for ≥8 hours)
- IMP was appropriately injected (as per weekly schedule)
- There was no intercurrent disease, which may jeopardize glycemic control (eg, infectious disease)
- Compliance to treatment was appropriate
- Compliance to diet and lifestyle was appropriate

If any of the above-mentioned explanations can reasonably explain the insufficient glycemic control, the Investigator should consider not initiating rescue medication(s) and should undertake appropriate action as follows:

- Assess FPG (ie, after the participant has fasted for ≥8 hours)

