- **Asymptomatic hypoglycemia:** Asymptomatic hypoglycemia is an event not accompanied by typical symptoms of hypoglycemia but with a measured plasma glucose concentration  $\leq 3.9$  mmol/L ( $\leq 70$  mg/dL).
- **Probable symptomatic hypoglycemia:** Probable symptomatic hypoglycemia is an event during which symptoms of hypoglycemia are not accompanied by a plasma glucose determination, but was presumably caused by a plasma glucose concentration  $\leq 3.9$  mmol/L ( $\leq 70$  mg/dL); symptoms are treated with oral carbohydrate.
- **Relative hypoglycemia:** (recently termed “pseudo-hypoglycemia”) is an event during which the person with diabetes reports any of the typical symptoms of hypoglycemia, and interprets the symptoms as indicative of hypoglycemia, but with a measured plasma glucose concentration greater than 3.9 mmol/L (70 mg/dL).

In addition to the threshold of plasma glucose of  $\leq 3.9$  mmol/L (70 mg/dL), documented hypoglycemia with a measured plasma glucose concentration between 3.0 to 3.9 mmol/L (54 to 70 mg/dL) and less than 3.0 mmol/L ( $< 54$  mg/dL) will also be analyzed (6).

Hypoglycemic events will be evaluated regardless of the time of onset during the study and time of the day.

In addition, hypoglycemia events will be evaluated at the following time periods defined by time of the day:

- **Nocturnal hypoglycemia defined by time of the day:** any hypoglycemia of the above categories that occurs between 00:00 and 05:59, regardless of whether participant was awake or woke up because of the event
- **Daytime hypoglycemia:** any hypoglycemia of the above categories that occurs between 06:00 and 23:59

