##### **Primary Analysis:**

The statistical analysis for the primary endpoint is described below.

The Baseline value is defined in [Section 2.1.1](#).

Analysis of the primary efficacy endpoint (change from Baseline to Week 56 in HbA1c) will be performed using the ITT population, using HbA1c measurements obtained during the study, including those obtained after IMP discontinuation or introduction of rescue therapy.

The primary efficacy endpoint of change in HbA1c from Baseline to Week 56 will be analyzed with missing values imputed by BOCF-like MI method for both efpeglenatide and dulaglutide groups, under the MNAR framework:

- For participants with missing HbA1c values at Week 56, the missing values will be imputed using a random draw from a normal distribution with mean equal to their Baseline HbA1c and the standard deviation equal to the pooled standard deviation calculated from the square root of the mean square error estimated from a regression model with Baseline HbA1c as the dependent variable and randomization strata and treatment as the covariates.

In this analysis, missing endpoint values will be imputed 10 000 times to generate 10 000 data sets with complete data. Each of the complete datasets after the imputation will be analyzed by the ANCOVA model with the treatment groups (efpeglenatide 4 or 6 mg, dulaglutide 1.5 mg), randomization stratum of screening HbA1c ( $<8.0$ ,  $\geq 8.0\%$ ), Visit 3 (Day 1) BMI ( $<30$  and

$\geq 30 \text{ kg/m}^2$ ), and geographical region (North America, Eastern Europe (including Hungary and Poland)) as fixed effects, and baseline HbA1c value as a covariate.

In case a baseline value needed for multiple imputations is missing, it will be imputed by the population mean at Baseline.

SAS pseudo-codes are provided in [Appendix A](#).

Results from each complete dataset will be combined to provide the adjusted mean change in HbA1c from baseline to Week 56 (regardless of treatment discontinuation or initiation of rescue therapy) for each treatment group, as well as the between-group difference (comparing each efpeglenatide group versus dulaglutide group) and the 95% CI for the difference. This will be implemented using MIANALYZE procedure in SAS. If the UB of the 2-sided 95% CI for the adjusted mean difference (efpeglenatide versus dulaglutide) in HbA1c change from baseline to Week 56 is  $\leq 0.3\%$ , the noninferiority will be declared.

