#### *2.4.4.4.6 Rescue therapy used during the treatment period until Weeks 30 and 56 (yes/no)*

Proportions of participants who used rescue therapy during the treatment period until Week 30 and until Week 56 respectively will be summarized.

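### The FPG rescue threshold after Week 30 is given as 10.1 mmol/L and as 180 mg/dL, which are not the same concentration, and neither document says which one governs

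*Protocol*

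**What the plan says.** Protocol section 6.1.2.2 refers to Table 3 for the rescue thresholds, which tighten in four steps. The last step, after the Week 30 visit, is "FPG >10.1 mmol/L (>180 mg/dL) or HbA1c ≥8.0"%. The step before it, after Week 12 through Week 30, is "FPG >11.1 mmol/L (>200 mg/dL) or HbA1c ≥8.5"%.

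The same limits serve three purposes: participants compare fasting SMPG with them, the central laboratory sends alerts against them (also section 6.3.1), and after an alert "a central laboratory re-test must be completed and confirmed as exceeding the threshold for rescue before rescue therapy is initiated". None of these passages names a unit. SAP section 2.1.2 mentions the applicable rescue threshold without restating it. Both documents provide for results in SI and conventional units, but that is a reporting convention and does not settle which figure triggers rescue.

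**The concern.** A limit written in two units should be one limit. Here a fasting glucose just above 180 mg/dL meets the criterion as written in mg/dL and fails it as written in mmol/L. Post-baseline FPG is masked from the investigator (section 6.3.1), so the alert is the main route to rescue, and whoever programs it must choose one of the two figures. Participants also need one limit for their home readings. If the laboratory and the meters, or different sites, worked from different figures, the rescue rule would not be uniform across the trial. The documents do not say which unit any site or meter used, so that last point is a possibility and not something that can be shown.

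**Working it through.** **Inputs.** The four FPG pairs are from Protocol Table 3. Two further glucose pairs are from Protocol section 8.2.5 ("plasma glucose concentration between 3.0 to 3.9 mmol/L (54 to 70 mg/dL"). The documents give no conversion factor. I assume 18.016 mg/dL per mmol/L (from the molar mass of glucose) and vary it from 18.0 to 18.0182.

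**Formulas.** mmol/L = mg/dL ÷ 18.016; mg/dL = mmol/L × 18.016.

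| Pair as printed (mmol/L; mg/dL) | Implied factor | mg/dL converted to mmol/L | mmol/L converted to mg/dL | Agrees |
|---|---|---|---|---|
| 15.0; 270 | 18.00 | 14.99 → 15.0 | 270.2 → 270 | yes |
| 13.3; 240 | 18.05 | 13.32 → 13.3 | 239.6 → 240 | yes |
| 11.1; 200 | 18.02 | 11.10 → 11.1 | 200.0 → 200 | yes |
| **10.1; 180** | **17.82** | **9.99 → 10.0** | **182.0 → 182** | **no** |
| 3.9; 70 | 17.95 | 3.89 → 3.9 | 70.3 → 70 | yes |
| 3.0; 54 | 18.00 | 3.00 → 3.0 | 54.0 → 54 | yes |

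**Sensitivity to the factor.** Across 18.0 to 18.0182, 10.1 mmol/L is 181.8 to 182.0 mg/dL and 180 mg/dL is 10.00 to 9.99 mmol/L. At 18.0 exactly, 13.3 mmol/L converts to 239.4 mg/dL, but 240 mg/dL still rounds to 13.3 mmol/L. The post-Week-30 row is the only one that fails in both directions.

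**Rounding.** Values that round to 10.1 mmol/L run from 10.05 × 18.016 = 181.1 to 10.15 × 18.016 = 182.9 mg/dL. Values that round to 180 mg/dL run from 179.5 ÷ 18.016 = 9.96 to 180.5 ÷ 18.016 = 10.02 mmol/L. The two ranges do not overlap.

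**Using only the protocol's own pairs.** The extreme implied factors among the five consistent pairs are 70/3.9 = 17.95 and 240/13.3 = 18.05. With these, 10.1 mmol/L is 10.1 × 70/3.9 = 181.3 to 10.1 × 240/13.3 = 182.3 mg/dL, and 180 mg/dL is 180 × 13.3/240 = 9.98 to 180 × 3.9/70 = 10.03 mmol/L. So the mismatch does not depend on the assumed factor. If the mg/dL limits are taken as exact and the mmol/L figures as rounded to one decimal, the first three rows of Table 3 need a factor between 17.98 and 18.06. The last row needs 180/10.15 = 17.73 to 180/10.05 = 17.91.

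**Values on which the two versions disagree.**

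| Fasting glucose, mg/dL | mmol/L | Above 180 mg/dL | Above 10.1 mmol/L, unrounded | Above 10.1 mmol/L, reported to one decimal |
|---|---|---|---|---|
| 180 | 9.99 | no | no | no |
| 181 | 10.05 | yes | no | no |
| 182 | 10.10 | yes | yes (10.102) | no |
| 183 | 10.16 | yes | yes | yes |

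**Exposure.** Of the scheduled fasting visits listed in Protocol section 5.3.1, only two fall after Week 30: "12 (Week 43), and 14 (Week 56), participants need to come to the study center in a fasting condition". Week 56 is the end of treatment, so one scheduled central FPG before then (Week 43) is exposed, plus any unscheduled test prompted by SMPG.

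**The case against.** The strongest reply is that the mismatch has almost no consequence. To matter, a participant's fasting glucose must fall in a band about 2 mg/dL wide after Week 30 and do so again on central re-test. HbA1c must be below 8.0%, poor compliance and intercurrent illness must be ruled out, and the investigator must still choose rescue, which section 6.1.2.2 permits but does not require. The operative number is whatever the central laboratory programmed. That specification is not in these documents and may be a single consistent limit. All of this stands, and it keeps the point minor, but it does not make the two printed figures agree.

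Three narrower replies also have some force. First, the post-Week-30 limit appears only once, so nothing in the text shows whether 10.1 or 180 was intended. The round mg/dL steps of 270, 240, 200 and 180 favor 10.0 mmol/L, but that is an inference. Second, mmol/L comes first in every row, which hints at the primary unit without making it a rule. Third, SAP section 2.3.1.2 records that the sponsor terminated the study on September 9, 2020, so a correction now mainly serves the record.

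It would also be too strong to say that rescue touches no tested endpoint. The primary analysis uses HbA1c values "including those obtained after IMP discontinuation or introduction of rescue therapy", and rescue can move those values. The completers analysis in SAP section 2.4.4.1 leaves out participants who started rescue.

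**Conclusion.** The concern holds. Table 3 states two different limits for the same criterion, about 0.1 mmol/L (2 mg/dL, roughly 1%) apart, and neither document resolves the difference. The arithmetic is secure: it needs only the conversion implied by the protocol's other glucose pairs. It is unlikely that any rescue decision changed, and no material effect on a tested endpoint is expected. The rescue endpoints themselves are exploratory and descriptive. SAP section 2.4.4.4.6 says "Proportions of participants who used rescue therapy during the treatment period until Week 30 and until Week 56 respectively will be summarized", and time to rescue is described by Kaplan-Meier curves. This is a minor correction to an operative threshold.

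**What to change.** Ask the sponsor which figure was intended. Unless 10.1 is confirmed, change the FPG part of the row to >10.0 mmol/L (>180 mg/dL), which keeps the round mg/dL steps. If 10.1 is confirmed, use >10.1 mmol/L (>182 mg/dL). The HbA1c part stays as it is. Then check that the central-laboratory alert and the participants' SMPG instructions carried that same limit. Because the study has ended early, state the limit that was actually applied wherever rescue use is reported, and do not carry the uncorrected row into another protocol.

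The cost is one figure in one table cell plus two checks. In a running trial it would also need a protocol amendment with ethics review (Protocol section 10.1.1), and if the laboratory had been using 10.1, moving to 10.0 would slightly lower the applied limit partway through. Design, sample size and analysis do not change.

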## **6.2 PREPARATION/HANDLING/STORAGE/ACCOUNTABILITY**

Investigators or other authorized persons (eg, pharmacists) are responsible for storing the IMPs in a secure and safe place in accordance with local regulations, labeling specifications, policies, and procedures.

Control of IMPs storage conditions, especially control of temperature (eg, refrigerated storage) and information on in-use stability and instructions for handling should be managed according to the rules provided by the Sponsor.

The expiry date is mentioned on the IMPs labels (when required by country regulation), and storage conditions are written on the IMPs labels and in the instruction leaflet.

The Investigator or designee must confirm appropriate temperature conditions have been maintained during transit for all study intervention received and any discrepancies are reported and resolved before use of the study intervention.

Only participants enrolled in the study may receive study intervention and only authorized site staff may supply or administer study IMP. All study IMP must be stored in a secure,

environmentally controlled, and monitored (manual or automated) area in accordance with the labeled storage conditions with access limited to the Investigator and authorized site staff.

The Investigator, institution, or the head of the medical institution (where applicable) is responsible for study IMP accountability, reconciliation, and record maintenance (ie, receipt, reconciliation, and final disposition records).

Further guidance and information for the final disposition of unused study IMP are provided in the Pharmacy Manual.

The Investigator, the hospital pharmacist, or other personnel allowed to store and dispense the IMPs will be responsible for ensuring that the IMPs used in the clinical trial are securely maintained as specified by the Sponsor and in accordance with applicable regulatory requirements. All IMPs will be dispensed in accordance with the Investigator's prescription and it is the Investigator's responsibility to ensure that an accurate record of IMPs issued and returned is maintained.

Any quality issue noticed with the receipt or use of an IMP/NIMP/device (deficiency in condition, appearance, pertaining documentation, labeling, expiration date, etc) must be promptly notified to the Sponsor. Some deficiencies may be recorded through a complaint procedure (see [Section 8.3.8](#)).

A potential defect in the quality of IMP/NIMP/device may be subject to initiation of a recall procedure by the Sponsor. In this case, the Investigator will be responsible for promptly addressing any request made by the Sponsor, in order to recall the IMP/NIMP/device and eliminate potential hazards.

Under no circumstances will the Investigator supply IMP/NIMP/device to a third party (except for IMP in case of DTP shipment, for which a courier company has been approved by the Sponsor), allows the IMP/NIMP/device to be used other than as directed by this clinical trial protocol, or dispose of IMP/NIMP/device in any other manner.

### **6.3 MEASURES TO MINIMIZE BIAS: RANDOMIZATION AND BLINDING**

All participants will be centrally assigned to randomized study intervention using interactive response technology (IRT) as summarized in the SoA ([Section 1.3](#)). Before the study is initiated, instructions on how to access IRT will be provided to each site.

A randomized participant is a participant who has been allocated to a randomized intervention regardless whether the intervention kit was used or not. A participant cannot be randomized more than once in the study.

Previously allocated IMP should not be redispensed to the participants.

### 6.3.1 Methods of blinding

The entire treatment period will be open-label for the drug (efpeglenatide, dulaglutide) and double-blind (for Investigators and participants) for the active doses (4 mg, 6 mg) of efpeglenatide. Efpeglenatide will be provided as a single-dose autoinjector and dulaglutide as a single-dose pen for self-injection. Each titration and treatment kit will be labeled with a unique number. The list of kit numbers will be generated by Sanofi.

In accordance with the study design, Investigators will remain blinded for the doses of efpeglenatide and will not have access to the randomization (dose) codes except under exceptional medical circumstances.

Members of the CEC will review and adjudicate events in a blinded manner (please also refer to Appendix 1 [[Section 10.1](#)]).

The Investigator will not have access to the data of the primary efficacy endpoint (ie, HbA1c) or FPG obtained after Baseline/Randomization visit (Day 1; Visit 3) as those data will be masked. If the central laboratory detects FPG above the rescue thresholds, the Investigator will receive an alert from the central laboratory (see [Section 6.1.2.2](#)). The HbA1c alerts will also be sent if a value is above threshold at the Week 12 visit (Visit 7) and onwards.

### 6.3.2 Randomization code breaking during the study

This section is applicable to those participants assigned to efpeglenatide arm.

The blind may be broken if, in the opinion of the Investigator, it is in the participant's best interest for the Investigator to know the study dose assignment. The Sponsor must be notified before the blind is broken unless identification of the study treatment is required for a medical emergency in which the knowledge of the specific blinded study treatment will affect the immediate management of the participant's condition (eg, antidote available). In this case, the Sponsor must be notified within 24 hours after breaking the blind. The date and reason that the blind was broken must be recorded in the source documentation and eCRF, as applicable.

Code breaking can be performed at any time by using the proper module of the IRT and/or by calling any other phone number provided by the Sponsor for that purpose. If the blind is broken, the Investigator should document the date, time of day and reason for code breaking. If the code is broken by the Investigator, the participant must withdraw from IMP administration. When documenting the reason for unblinding, the Investigator must not provide any detail regarding the nature of the IMP. The Investigator should not divulge IMP detail to the Sponsor's representative or to any staff members until database closure. Furthermore, when completing forms (eg, AE, SAE, adjudication information), the efpeglenatide dose should not be disclosed on the forms.

Randomization code breaking will also be performed during the analysis of the PK serum concentration samples and ADA samples in order to enable the laboratory to sort the samples (verum [dose group],) and start analyzing the samples (verum group only) while the study is still ongoing. Only the independent Sponsor representative, Project Manager, and lead scientist at the Bioanalytical laboratory, as well as the population PK analyst, will have access to the

randomization code to allow for the sorting of the efpeglenatide blood samples. The Bioanalytical laboratory and responsible personnel will follow the standard procedures to ensure the protection of the blind within the Sponsor's clinical team. The randomization code or the individual analytical results will not be disclosed to any clinical team personnel prior to the database lock.

The DMC will receive unblinded safety data from an independent statistician for review, which will be handled strictly confidentially. None of these reports may be delivered to unauthorized persons (Appendix 1 [[Section 10.1](#)]).

Refer to [Section 8.3.4](#) for suspected unexpected serious adverse drug reaction unblinding by the Sponsor.

## **6.4 STUDY INTERVENTION COMPLIANCE**

Measures taken to ensure and document treatment compliance and IMP accountability include the following:

- Proper recording of treatment kit number as required on appropriate eCRF page for accounting purposes
- All medication treatment kits (whether empty or unused) will be returned by the participant at each visit when a treatment dispensing is planned
- The Investigator or his/her delegate tracks treatment accountability/compliance comparing the treatment kit number recorded on the participant diary with the treatment kit number of returned treatment kits (whether empty or unused) and completes in the participant treatment log
- The monitor in charge of the study will then checks the data entered on the IMPs administration page of the eCRF by comparing them with the IMPs that have been retrieved and the participant treatment log form
- For the NIMP not provided by the Sponsor, tracking and reconciliation will be documented in participant's source documents and medication reported in appropriate eCRF pages

### **6.4.1 Return and/or destruction of treatments**

A detailed treatment log of the destroyed IMPs will be established with the Investigator (or the pharmacist) and countersigned by the Investigator and the monitoring team. The Investigator will not destroy the used and unused IMPs unless the Sponsor or delegate provides written authorization. For NIMP reimbursed by the Sponsor, tracking and reconciliation will be completed by the Investigator (or the pharmacist, if appropriate) as per local requirements.

Destruction of IMP is strongly encouraged at site level, nevertheless, if the site is not able to destroy IMP or destruction of IMP is not allowed in the country, all treatment kits will be retrieved by the Sponsor.

At selected sites in US only, at least 120 used efpeglenatide autoinjectors that functioned normally (with no PTCs) will be returned to the Sponsor using a defined return process.

Sharp containers containing all used autoinjectors that are not affected by a complaint or the specified return process will be brought back to the site by the study participants for the purpose of destruction.

Separate instructions will be supplied to the site and participants, in accordance with local law as well as regulatory requirements.

